9.0 Vulnerable Populations

PROTOCOL TITLE: Prospective Randomized controlled study comparing liposomal bupivacaine to bupivacaine interscalene blocks for arthroscopic rotator cuff repair surgery

VERSION DATE: 8/5/2020

9.1 Vulnerable Populations:

- Children
- Pregnant women/Fetuses/Neonates
- Prisoners
- Adults lacking capacity to consent and/or adults with diminished capacity to consent, including, but not limited to, those with acute medical conditions, psychiatric disorders, neurologic disorders, developmental disorders, and behavioral disorders
- Approached for participation in research during a stressful situation such as emergency room setting, childbirth (labor), etc.
- Disadvantaged in the distribution of social goods and services such as income, housing, or healthcare
- Serious health condition for which there are no satisfactory standard treatments
- Fear of negative consequences for not participating in the research (e.g. institutionalization, deportation, disclosure of stigmatizing behavior)
- Any other circumstance/dynamic that could increase vulnerability to coercion or exploitation that might influence consent to research or decision to continue in research
- Undervalued or disenfranchised social group
- Members of the military
- Non-English speakers
- Those unable to read (illiterate)
- Employees of the researcher
- Students of the researcher
- None of the above

9.2 Additional Safeguards:

10.0 Local Number of Participants

10.1 Local Number of Participants to be Consented: 90 patients as we expect a dropout or loss to follow up of 20%

11.0 Local Recruitment Methods

11.1 Recruitment Process: Patients will be recruited from the group of adult surgical patients at the University of Minnesota undergoing RCR and receiving an interscalene block. Patients will be approached at the preoperative assessment clinic at the Clinic and Surgery Center if possible by a research staff member to determine their interest in participation. If they decide to be a participant they will be consented and given a copy of their consent form for their records and a consent will be scanned and placed into EPIC. If the patient is scheduled for a midday surgery, the research staff will approach them in the preoperative surgical

PROTOCOL TITLE: Prospective Randomized controlled study comparing liposomal bupivacaine to bupivacaine interscalene blocks for arthroscopic rotator cuff repair surgery

VERSION DATE: 8/5/2020

area. These patients will have significant time to review the study with research staff as well as the physicians performing the procedure due to the fact they arrive several hours prior to their scheduled surgery. All subjects will have enough time to ask questions about the study and the potential risks involved regardless of which venue they are consented.

11.2 Identification of Potential Participants: Patients will be identified by members of the treatment team in either the surgeon's clinic, pre-assessment clinic, or preoperative area. Patients who have opted out of research will not be asked to participate in the study. Patients will be approached to consent for the study by a surgeon, anesthesiologist, or member of the research team. Patients who agree to participate in the study will sign both a study consent and HIPAA authorization allowing the use of specified information contained in medical records for research purposes.

11.3 Recruitment Materials: N/A

11.4 Payment: No payment will be provided to patients.

12.0 Withdrawal of Participants

12.1 Withdrawal Circumstances: Subjects who have consented prior to the day of surgery and for some reason choose not to participate will be withdrawn and a notation will be made in the study records and these people will be considered screen failures. The surgeon may choose to withdraw the patient from the study prior to surgery for any medical reason or if they suffer a major life threatening adverse event.

12.2 Withdrawal Procedures: If the patient is withdrawn from study prior to the procedure, they will be noted in study records as screen failures. If they undergo the procedure and they decide they no longer want to be a part of the study or withdrawn by the physician, they will be withdrawn and no further data will be collected. This will also be noted in the study documentation.

12.3 Termination Procedures: If the study is terminated for any reason, or there is more than 5 % major adverse events the data that is already collected will be stored in a secure location only accessible to research personnel on this study. No further data will be collected if the study is terminated.

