4.5 Biosafety: n/a

4.6 Stem Cells: n/a

5.0 Procedures Involved

5.1 Study Design: **Level I randomized prospective outcomes study comparing two groups of patients. One group will receive LB plus bupivacaine for an interscalene block. The other will receive bupivacaine for an interscalene block injection.**

Study Procedures: Patients will be identified in the pre-operative time period by the surgeons and if possible will be consented by the research coordinator or research assistant. If that is unable to be accomplished the patient will be introduced to the study and given a copy of the consent form to evaluate prior to surgery. On the day of surgery, the research coordinator, research assistant or primary or sub investigators will determine if the patient has any questions so that they can be answered. After discussion with the person obtaining consent, consent will be obtained in the pre-operative area. A random number generator will be used to determine if the patient will have LB plus bupivacaine or bupivacaine for their interscalene block. The primary investigator will access the number generator in the pre-op area immediately prior to block placement. The website www.random.org will be used as the random number generator.

Treatment technique:

All patients will receive preoperative oral multimodal medications consisting of acetaminophen 975 mg and gabapentin 300 mg.

After completion of the preoperative process the patient will be placed in the supine position with the head of the bed elevated 30 degrees with standard ASA monitors applied. Sedation will be provided with midazolam 0-2 mg and propofol 50 mg. The

PROTOCOL TITLE: Prospective Randomized controlled study comparing liposomal bupivacaine to bupivacaine interscalene blocks for arthroscopic rotator cuff repair surgery

VERSION DATE: 8/5/2020

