interscalene groove will be identified with the ultrasound. Using sterile technique, a 21g Nerve block needle will then be inserted and advanced under ultrasound guidance until it is in the interscalene groove. Once in the interscalene, 20 mL of local anesthetic will be injected, with 10 mL deposited at the top of the brachial plexus and 10 mL at the bottom. In the study group, 5 mL of each 0.5% bupivacaine and LB will be injected at each location. The control group will have 20 mL of 0.5% bupivacaine divided between the injection sites (10 mL at each site). The patient will be monitored in the preoperative area until he/she is brought into the operating room for their procedure. A working block prior to surgery will be confirmed via sensory testing of the shoulder.

All patients will undergo a standard induction with propofol 1.5-3.0 mg/kg, ondansetron 4 mg, dexamethasone 10 mg and ketamine 0.25 mg/kg. A MAC or general LMA or ETT will be placed and an opioid sparing technique will occur. Standardized maintenance will be a propofol infusion without neuromuscular blockers. 25-50 mcg of IV Fentanyl will be utilized for increases in heart rate greater than 20% or increases in systolic blood pressure above baseline.

Once in the operating room the surgeon will use an additional 10 mL of 0.25% bupivacaine for skin, subcutaneous, and intraarticular injection.

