When the operation is complete, the patient will be woken up and brought to the PACU. There the patient will receive IV fentanyl for a pain score of greater than 7 (50 mcg of Fentanyl x 2 if needed). If more than 100 mcg of fentanyl is given and pain still remains above a 7 then IV hydromorphone will be used (max dose of 1 mg and given in increments of 0.3 mg q 10 minutes prn severe pain). Once the patient is able to tolerate oral medications a dose of 5 mg of oral oxycodone (or 2 mg of oral hydromorphone if allergic to oxycodone) will be given if their pain score is greater than 4 (on the Visual Analog Scale). Once the patient meets discharge criteria, they will be discharged home where each day they will fill out a pain diary. Additionally, a member of the research team will call the patient for signs of complications and ask the patient their current pain score, total opioid pills taken and non-opioid pain medication taken at 24, 48, and 72 hours postoperatively. Additionally, they will perform a Quality of Recovery Score survey at 72 hours, and 14 days postoperatively. An Ultrasound of the diaphragm will be completed by a blinded anesthesiologist in the PACU to assess diaphragm function. All patients will be discharged with instructions to take acetaminophen 975 mg q8 hours & ibuprofen 600 mg q6 hours. Additionally they will have opioid pain medication to take as needed for pain greater than 4. They will either have hydromorphone 2mg, 30-40 pills, with dosing being 1-2 pills q4 hours prn severe pain. Or they will have a prescription for oxycodone 5 mg, 30-40 pills, dosing 1-2 pills q 4 hours prn severe pain.

Enrollment procedures: Patients will be identified in the pre-operative time period by the surgeons and if possible will be consented by the research coordinator or research assistant. If that is unable to be accomplished the patient will be introduced to the study

PROTOCOL TITLE: Prospective Randomized controlled study comparing liposomal bupivacaine to bupivacaine interscalene blocks for arthroscopic rotator cuff repair surgery

VERSION DATE: 8/5/2020

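### Section 12.2 ends data collection after a physician withdrawal even when the patient still consents, and its screen-failure rule does not except randomised patients

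*Combined protocol and SAP*

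**What the plan says.** **Withdrawal after the procedure.** Section 12.2 covers two cases in one sentence: the patient no longer wishes to take part, or a physician withdraws the patient. The consequence is the same for both: "or withdrawn by the physician, they will be withdrawn and no further data will be collected".

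**Grounds for physician withdrawal.** Section 12.1 leaves this to the surgeon's discretion: "withdraw the patient from the study prior to surgery for any medical reason or if they suffer a major life threatening adverse event".

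**Withdrawal before the procedure.** Section 12.2: "If the patient is withdrawn from study prior to the procedure, they will be noted in study records as screen failures".

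**Time of randomisation.** Section 5.1: "The primary investigator will access the number generator in the pre-op area immediately prior to block placement".

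**Planned follow-up.** Section 5.1 has calls recording "total opioid pills taken and non-opioid pain medication taken at 24, 48, and 72 hours postoperatively", Quality of Recovery surveys at 72 hours and day 14, and an assessment for block complications. The listed complications include sensory loss or arm weakness lasting more than 3 days. Sections 5.1 and 5.3 end participation at day 14 but provide for chart monitoring, with a note of readmission for pain, up to day 30.

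**Analysis.** Section 15 names no analysis set and no method for missing data. Section 17.2 puts safety data on a case report form but does not say whether this continues for withdrawn patients.

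**The concern.** A patient who withdraws consent has asked the study to stop, and ending collection then is not in dispute. A physician's decision to withdraw a patient is different. The patient has not asked for follow-up to end, and the reason for withdrawal may be related to the outcome. Ending collection in that case discards primary and safety data that the patient was still willing to give.

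Two things are at stake. The later course of a complication can go unrecorded, and complications defined by their duration can be undercounted. The 72-hour opioid total can also be incomplete for a randomised, operated patient, with no stated way to handle it.

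The screen-failure wording raises a related but weaker question. A screen failure is normally someone who never entered the comparison. Here the label has no exception for a patient whose random number has already been drawn, so a randomised patient could drop out of the account of the arms.

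**Working it through.** **1. The plan's own figures.** The documents give no expected number of physician withdrawals. The only attrition figure is the 20% in section 10.1: 70/(1 − 0.20) = 87.5, rounded up to 88, against the stated 90; and 90 × 0.80 = 72. This allowance protects patient numbers. It does not address bias or lost safety follow-up. The 80% power in section 15.2 cannot be reproduced, because no effect size, SD or significance level is given.

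**2. Does the data stop depend on how section 12.1 is read?**

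| Reading of 12.1 | Stated ground for withdrawal after surgery | Effect of 12.2 |
|---|---|---|
| The before-surgery limit governs only the medical-reason ground | Life-threatening event | Collection can stop for a reason related to outcome |
| The before-surgery limit governs both grounds | None | Collection still stops; the reason is unspecified |

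The stop applies either way. Only its link to severe events changes.

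**3. Data lost per physician-withdrawn patient after surgery.**

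| Time of withdrawal | Opioid calls lost (of 3) | 72-hour total | Quality of Recovery surveys lost |
|---|---|---|---|
| Before the 24-hour call | 3 | Incomplete | 72 h and day 14 |
| Between the 24 and 48-hour calls | 2 | Incomplete | 72 h and day 14 |
| Between the 48 and 72-hour calls | 1 | Incomplete | 72 h and day 14 |
| After 72 hours, before day 14 | 0 | Complete | Day 14 |

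In the first three rows the patient also cannot be recorded with a complication defined as lasting more than 3 days.

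**4. Safety illustration.** Assume 70 patients in equal arms, 70/2 = 35 (no allocation ratio is stated). One unrecorded case of weakness lasting more than 3 days changes an arm's rate from 1/35 = 2.9% to 0/35 = 0%.

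**5. Primary-outcome illustration.** Let k operated patients be lost from one arm of 35, with opioid use differing from the rest of that arm by d SD. Shift in the arm mean = k × d/35.

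- k = 1, d = 1: 1/35 = 0.029 SD
- k = 3, d = 2: 6/35 = 0.171 SD

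With a two-sided 5% t-test and 80% power at 35 per arm, the detectable difference is 0.679 SD. The normal approximation gives (1.960 + 0.842) × √(2/35) = 0.670. The shifts are 0.029/0.679 = 4% and 0.171/0.679 = 25% of the detectable difference. The values of k and d, the equal allocation, the test and the 5% level are all assumptions.

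**6. Who can be labelled a screen failure after randomisation?** The order in section 5.1 is random number, block, wait, operating room.

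- If *procedure* means the operation, patients already randomised and blocked are included. Section 5.1 uses the word this way after the block: "The patient will be monitored in the preoperative area until he/she is brought into the operating room for their procedure".
- If it means the block, only patients between the random number and the injection are included. Section 11.1 leaves this possible, with its reference to patients reviewing the study with research staff "as well as the physicians performing the procedure".

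The first reading has the better textual support, but the word is not defined. Neither reading excepts randomised patients.

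**The case against.** The strongest reply is that the consequences are uncertain and few patients are involved. Several parts of it stand.

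- **Worst events.** A reader might infer that the plan stops collection in the patients with the most severe events. The documents do not establish this. The before-surgery limit in section 12.1 can govern both grounds, and withdrawal is the surgeon's choice, so a life-threatening event does not by itself end collection. Section 5.1 would also have the event itself recorded; what can be lost is its later course.
- **Day 30.** A reader might infer that the readmission note is certainly lost. Sections 5.1 and 5.3 provide for that note after participation has ended, so it is unclear whether the data stop reaches it. It may be lost.
- **Screen failures.** A reader might infer that randomised patients will be removed from the trial without trace. Section 12.2 requires the withdrawal to be noted in study records, and the screen-failure sentence in section 12.1 is narrower, covering patients consented before the day of surgery who choose not to take part. A cancelled operation yields no 72-hour postoperative total, so bias in the primary outcome needs a patient who was randomised, withdrawn and still operated on.
- **Upper illustration.** Losing 3 of 35 (8.6%) to life-threatening events is unlikely. Section 13.1 lists the individual serious bupivacaine effects at under 2%. At an assumed 2% risk, the binomial probability of three or more in 35 is 1 − (0.493 + 0.352 + 0.122), about 3%.
- **Unseen forms.** The consent and HIPAA forms were not available for review and may govern the use of records after withdrawal.

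None of this changes the rule itself. Section 12.2 ends collection after a physician withdrawal, and no other section restores it.

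**Conclusion.** The point holds in a limited form. The rule for physician withdrawal is explicit and does not depend on how section 12.1 is read. It can leave the primary opioid total incomplete, prevent the recording of complications lasting more than 3 days, and lose the day 14 assessment in patients who have not withdrawn consent. Confidence in this part is high.

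The screen-failure part is secondary and held with lower confidence, because it rests on an undefined word and a short interval before surgery.

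The number affected is unknown and probably small. On the assumptions shown, the shift in an arm mean is 0.03 to 0.17 SD, and the upper end is improbable if withdrawals follow only life-threatening events. The documents therefore do not support a claim that the primary comparison is seriously compromised. The case for change rests mainly on safety follow-up, where a single patient can alter an arm's rate, and on the low cost of the correction.

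**What to change.** 1. **Section 12.2, data stop.** Limit it to withdrawal of consent. After a physician withdrawal, continue the planned opioid calls, complication assessment, day 14 survey and chart review unless the patient withdraws consent. Keep data already collected.
2. **Sections 12 and 15, populations.** Define a screen failure as a consented patient for whom no random number was drawn. Report every randomised patient by assigned arm, with the reason for any withdrawal. Analyse as assigned those who undergo the operation. Include all blocked patients in the safety analysis.

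The sponsor should also say which reading of section 12.1 is meant, although neither change depends on the answer.

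**Cost.** Wording in sections 12 and 15, a few extra contacts using calls and chart review already planned, and possibly a matching line in the consent and HIPAA forms.

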and given a copy of the consent form to evaluate prior to surgery. On the day of surgery, the research coordinator, research assistant or primary or sub investigators will determine if the patient has any questions so that they can be answered. After discussion with the person obtaining consent, consent will be obtained in the pre-operative area. Subjects interested in the study will be presented with consent and Health and Insurance Portability and Accountability Act (HIPAA) forms. The patient will review the forms with the surgeon, research staff, or anesthesiologist. Subjects will be reminded that participation is completely voluntary, and that they may stop participation at any time without question or penalty. The surgeon, research staff, or anesthesiologist will answer any questions that the subjects may have about the study. If the patient decides to participate, they will be asked to sign the consent and HIPAA forms. One copy will be saved for study records, and the subject will be provided with a copy of the forms for their own records. The patient will then have an opportunity to ask any questions of the surgeon regarding the treatment option that has been selected. All forms will be locked and stored in a file cabinet in the research department. Enrollment will proceed from July 2018 to July 2019. Enrolling consecutive patients will help reduce selection bias.

Assessments: Post-operatively patients will be evaluated at 2 and 6 hours post-operatively by a blinded research staff. This person will not be aware of the patient's mode of analgesia. The patients will be contacted via in person assessment or via telephone at 24, 48, and 72 hours +/- 5 hours. Patients will be asked to rate their pain on scale of 0-10. The amount of opioids used by the patient will be recorded as will any other adjuvant pain medication used. The time in phase 1 and phase 2 of PACU will be recorded. The patients will be asked at 72 hours post-injection if they would undergo interscalene block with their medication again or if they would opt for a different form of pain management. Patients will fill out a Quality of Recovery Survey at 72 hours and 14 days, and be assessed for block related complications at this time. All complications will be recorded including:

- Failure of the block
- Wound infections
- Subsequent procedures

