- Complications related to placement of the interscalene block including nerve injury, prolonged sensory loss greater than 3 days, prolonged arm weakness greater than 3 days
- Opioid related side effects of nausea and/or vomiting
- Local anesthetic toxicity as evidenced by seizures or cardiovascular collapse without other reasonable etiology

Patients will be asked in the daily phone call if they or their family contacted anyone (any health care professional) regarding their pain overnight and that will be documented.

All data will be recorded on the Clinical Diagnostic Sheet and will then be given to the research coordinator for manual data entry. Data collection will continue until POD #14. At that time study participation will be terminated. Should patients be re-admitted to the

PROTOCOL TITLE: Prospective Randomized controlled study comparing liposomal bupivacaine to bupivacaine interscalene blocks for arthroscopic rotator cuff repair surgery

VERSION DATE: 8/5/2020

hospital in the next two weeks (Up to POD #30) for pain, a notation will be made in study records.

An analysis of the total cost of analgesics will be tabulated at the conclusion of the study to determine the most cost effective treatment option as this will be added into the cost of hospitalization including the number of days each patient spent in the hospital.

Blinding Procedure: The research assistant in this study will be blinded to the method of analgesia for the patient. The research assistant will assess pain one time per day. This person will not be responsible for any clinical testing and will record all data in the protected database daily. They will not have any access to the patients' clinical records or chart. **Any questions from the patient will be referred to the on-call resident or staff on call.**

5.2

Describe:

- The interscalene block is standard of care for patients and would be performed regardless of patient's participation in the study. All patients still would get preoperative multimodal treatment as well as an opioid sparing anesthetic.
- Patients would be required to take a dose of acetaminophen 975 mg oral and gabapentin 300 mg oral prior to surgery. They would then be required to receive an interscalene block with either liposome bupivacaine and bupivacaine or bupivacaine. Intraoperatively they would be required to receive propofol, lidocaine, ondansetron, dexamethasone, and ketamine for induction of anesthesia.

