- In addition to the surveys used to measure subjective and objective outcome, other data will be collected during patient interviews including:
 - Demographic data
 - Age
 - Weight
 - ASA class
 - Duration of surgery
 - Pain Score at 2, and 6 hrs after surgery and once a day thereafter
 - Length of stay in recovery room both phase 1 and phase 2
 - Amount of opioids given intraoperatively and post-operatively
 - Satisfaction with treatment
 - Quality of recovery survey at 72 hours and 14 days
 - Non opioids used
 - Adverse events
 - Length of hospital stay

PROTOCOL TITLE: Prospective Randomized controlled study comparing liposomal bupivacaine to bupivacaine interscalene blocks for arthroscopic rotator cuff repair surgery

VERSION DATE: 8/5/2020

- 5.3 Study Duration: We anticipate the study to take from June 2018 to June 2019. Patients will be in the study for 14 days and then their chart monitored for up to 30 days post surgery. The data analysis should take one month after full enrollment of the study.
- 5.4 Individually Identifiable Health Information: This study involves the use of individually identifiable health information. Please see attached HIPAA authorization form.
- 5.5 Use of radiation: n/a
- 5.6 Use of Center for Magnetic Resonance Research: n/a

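### Section 12.3 ends all data collection if the study is terminated, with no exception for patients who have already had the block and have not withdrawn

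*Combined protocol and SAP*

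**What the plan says.** Section 12.3 (Termination Procedures) has two sentences. The first opens "If the study is terminated for any reason, or there is more than 5 % major adverse events" and goes on to say that "the data that is already collected will be stored in a secure location only accessible to research personnel on this study". The second is the flat rule: "No further data will be collected if the study is terminated". Neither separates stopping enrolment from stopping follow-up.

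The planned follow-up is in Section 5.0. Section 5.1 (Assessments) schedules contacts at 24, 48 and 72 hours and then states: "Patients will fill out a Quality of Recovery Survey at 72 hours and 14 days, and be assessed for block related complications at this time". It adds: "Data collection will continue until POD #14". Section 5.3 extends this: "Patients will be in the study for 14 days and then their chart monitored for up to 30 days post surgery". The complications listed in 5.1 include nerve injury, wound infection, subsequent procedures, and sensory loss or arm weakness lasting more than 3 days.

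Section 12.2 has a similar rule for individuals who leave after the procedure: "they will be withdrawn and no further data will be collected". That rule is triggered by the patient's or physician's decision about one person. Section 12.3 is triggered by a decision about the whole study.

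Section 17.2 provides for monthly data to a monitoring committee, which meets and makes recommendations if adverse events show a pattern. It says nothing about completing follow-up after a stop.

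**The concern.** Terminating a trial of a single injection stops new exposure but leaves existing exposure as it is. A patient blocked the day before termination remains at risk of every complication that the protocol lists, has not withdrawn, and has been withdrawn by nobody. Under 12.3 as written, the study would nevertheless collect nothing more on that patient.

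The complications most likely to be missed are the late ones. Sensory loss or weakness beyond 3 days cannot be identified in someone whose data stop before day 3. If the stop was prompted by suspected harm, the count of late events would be too low in the most recently treated patients, and the committee would judge the signal on less complete data. For patients still inside 72 hours, the primary opioid total would also be incomplete. Data not collected at the time may not be recoverable later.

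**Working it through.** **Text check.** The point rests on wording, and the plan gives no figure of its own to reproduce. Each planned item is set against 12.3:

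| Planned item | Where planned | If the study terminates first |
|---|---|---|
| 24, 48, 72 h contacts | 5.1 | not collected |
| QoR survey and complication assessment, 72 h and day 14 | 5.1 | not collected |
| Chart check to day 30 | 5.1, 5.3 | not collected |
| Treatment for injury | 19.1, 23.0 | remains available (care, not study data) |

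No other section restores study data collection after termination.

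**Number of patients affected (illustration).** Inputs:
- N = 70 patients (15.2; 23.0 also gives 70 as the number to enrol).
- Accrual period D = 365 days (5.1 and 5.3 each give a span of about 12 months) or 91 days (23.0, three months). The two plans conflict.
- Centre volume of about 300 rotator cuff repairs a year (23.0).
- Assumption: even accrual, with termination at a time when the window is full.

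Expected number inside a window of w days = N × w / D.

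| Window | 12 months | 3 months |
|---|---|---|
| 72 h (3 days) | 70 × 3/365 = 0.6 | 70 × 3/91 = 2.3 |
| 14 days | 70 × 14/365 = 2.7 | 70 × 14/91 = 10.8 |
| 30 days | 70 × 30/365 = 5.8 | 70 × 30/91 = 23.1 |

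**Plausibility of the 3-month column.** The centre's volume in 91 days is 300 × 91/365 = 74.8 cases. Enrolling 70 would need 70/74.8 = 94% of them, so this column is an upper limit. Treating 90 in that time would exceed the whole volume.

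**Slower accrual.** The version is dated 8/5/2020, and 15.2 still speaks of continuing to enrol towards 70. If enrolment began on 1 July 2018 (an assumption; 5.1 gives only the month) and the date is read as 5 August 2020, 766 days had passed. The 14-day window would then hold at most 70 × 14/766 = 1.3 patients.

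**Scale.** Among 70 patients, 3 events are 4.3% and 4 are 5.7%. One missed late event is 1.4 percentage points, which is enough to move the rate across 5%.

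**The case against.** The strongest case on the other side accepts the wording of 12.3 and disputes what follows from it.

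- **The 5% clause.** A reader might infer that exceeding 5% major adverse events automatically ends data collection. The text does not say so. The clause is joined to termination by 'or' and governs storage of existing data: "there is more than 5 % major adverse events the data that is already collected will be stored in a secure location". The ban on further data applies only if the study is terminated, and 17.2 speaks only of committee recommendations. This stands. The point survives because termination for any reason includes a harm-based stop.
- **Care.** A reader might infer that patients are left without follow-up care. Sections 19.1 and 23.0 keep treatment for injury available, so this inference fails.
- **The committee.** It would be too strong to say that it could not assess a signal. Data already collected are kept, and most treated patients could have passed day 14. Recent patients would be cut off by calendar date in both arms, and the documents give no basis for claiming a systematic bias between arms. What stands is less complete data and an undercount of late events.
- **Size.** Larger counts come from putting 90 patients into 3 months, which the stated centre volume rules out. The 30-day counts also overstate the safety loss, because the only specific item after day 14 is a note of readmission for pain. The 72 h loss is about 1 to 2 patients in a trial already stopped.
- **Contingency.** Nothing is lost unless the study is terminated, and the documents give no probability of that. This limits the severity but does not remove the gap.

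**Conclusion.** The point holds as a contingent gap in the plan that should be closed. Section 12.3, followed as written, stops study data collection on treated patients who have not withdrawn, and no other section reverses this. That conclusion depends on no calculation.

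Its size is modest. With even accrual of 70 patients, about 3 would miss the day-14 assessment under the 12-month plan and at most about 11 under the 3-month plan, with fewer if accrual is slower. About 1 to 2 would have an incomplete 72 h primary outcome. These counts rest on the even-accrual assumption and on two accrual periods that the document does not reconcile.

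The documents do not establish that crossing 5% terminates the study. That ambiguity is a second, smaller defect in the same section, to be settled by the sponsor.

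**What to change.** Replace the last sentence of 12.3 with:

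*If the study is terminated, enrolment, randomisation and new study blocks stop. Patients who have already received a study block and have not withdrawn consent complete the already scheduled 24, 48 and 72 h contacts, the day-14 assessment and the chart check to day 30, and these data are reported by arm to the monitoring committee and in the final report.*

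Reconcile 12.3 with 5.1, 5.3 and 17.2. In the same amendment, make clear whether the 5% major-adverse-event clause is a termination trigger or only a condition for storing data, and how it relates to the committee's recommendations in 17.2. This review takes no position on what that rule should be.

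The change does not touch 12.2, whose rule for individual withdrawals, including those by the physician, needs its own check.

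Cost: one amended sentence and a clarification. If the study is terminated, existing research staff finish a small number of calls and chart checks already scheduled. No new procedure is added, and patients may still decline.
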